2.11 Operative Procedures

All operative procedures, regardless of cause, will be reported per randomized treatment arm. The report will include the number and percentage of subjects who receive an operative procedure after implant and the total number of procedures that occur within one year of the initial device implant. The reason for the operation will also be summarized.

2.12 Quality of Life and Functional Status

Quality of life and functional status will be measured at baseline, 6 months and 12 months. Results will be reported per randomized treatment group:

EQ-5D: The Visual Analog Score (VAS) will be summarized using descriptive statistics. A table will be created with the results of the EQ-5D questions

NYHA Class: Results will be categorically presented by time interval and treatment arm

6-Minute walk test (6MWT): Distance walked at each time interval will be descriptively presented. Subjects who are unable to walk due to heart failure will be imputed a score of 0. All other missing data will be ignored.

2.13 Stratification by Pre-implant Aspirin Use

The primary endpoint will be analyzed by stratifying subjects that are on aspirin pre-implant of the HM3 versus subject who are not using aspirin pre-implant.

2.14 Subject Early Termination

The reason for early termination will be summarized for each randomized treatment group. Causes of death will also be summarized by treatment group.

2.15 Protocol Deviation

Protocol deviations will be summarized by major and minor categories for subjects in whom a protocol deviation was reported. Major protocol deviations will include:

Statistical Analysis Plan

- withdrawal of the treatment arm antithrombotic regimen without clinical reasons
- additional antiplatelet medications added to the treatment arm antithrombotic regimen
- enrollment or randomization of patients who do not meet eligibility requirements
- informed consent deviations, except inadvertent incorrect dating.

3.0 DOCUMENTATION AND OTHER CONSIDERATIONS

4.0 ACRONYMS AND ABBREVIATIONS

Acronym or Abbreviation	Complete Phrase or Definition
CEC	Clinical Events Committee
CIP	Clinical Investigation Plan
CRF	Case Report Form
DSMB	Data Safety Monitoring Board
HCS	Hemocompatibility Score
HM3	HeartMate 3
ITT	Intent To Treat
LVAS	Left Ventricular Assist System
MRS	Modified Rankin Score
NIM	Non-Inferiority Margin
SAE	Serious Adverse Event
SAP	Statistical Analysis Plan
TTR	Time in Therapeutic Range

Statistical Analysis Plan

6.0 APPENDICES

[REDACTED]

[REDACTED]

[REDACTED]

[REDACTED]

[REDACTED]

Statistical Analysis Plan

APPENDIX B: Device Position Substudy

A substudy is proposed to develop and validate the use of a radiopaque surgical marker placed on the anterior surface of the aortic root below the sino-tubular ridge of the aorta just above the ostia of the right coronary artery to be used as a surrogate anatomical reference or landmark to more optimally assess HeartMate 3 inflow cannula position. The substudy will include subjects enrolled in the ARIES HM3 study who also meet eligibility requirements for this substudy at participating centers. Validation will be performed by assessing:

1. Safety and feasibility assessment of the radiopaque surgical marker will be made using anteroposterior (AP) and lateral radiographs captured prior to discharge (but within 30 days of implant) and at the 3-month follow up visit. The following assessments will be descriptively presented as the number and percentage of subjects for each category: successful placements, successful visualizations, and gross migrations. Adverse events related to the clip or placement procedure will be presented as the number and percentage of subjects enrolled in the substudy and total number of events.
2. The angular position of the canula relative to the marker will be measured from the AP view, and the distance of the marker to the axial alignment of the canula will be measured from the lateral view. The cannula position relative to the radiopaque marker and cannula positional changes over time will be descriptively and graphically summarized from both the AP and lateral radiographs. These measurements will be summarized as mean with standard deviation, and by quartiles, minimum and maximum values.

The radiographs recorded at both pre-discharge and 3 months will be reviewed by an independent evaluator and assessed visually for cannula position at both time points along with potential significant change in position from pre-discharge to 3 months. Visual assessments will be categorized and summarized as count and percentage of subjects enrolled in the substudy.

3. Patients may also be grouped into clusters with each cluster representing different levels of change in cannula position. Comparisons of adverse clinical outcomes and functional capacity including the following will be made between clusters:
 - Adverse Events: Mortality, Stroke, Pump Thrombosis, Bleeding, Major HRAE, HRAE, Right Heart Failure, Cardiac Arrhythmia
 - Major thrombotic and major hemorrhagic events
 - Hospitalizations
 - Index Hospitalization and ICU Length of Stay; All Cause readmission; Number of readmissions; Days out of the hospital vs in-hospital
 - RHF Caused Hospitalizations
 - 6 Minute Walk Test Distance as a surrogate for LV unloading
 - Change over time, cumulative 6MWT distance (post implant only)
 - EQ-5D-5L
 - NYHA Classification
 - Effect of Treatment Arm designation on AEs as Sensitivity Analysis

Clinical significance can then be interpreted with the results of comparison.

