6.3 Study Activities and Procedures

The assessments in table 2 will occur throughout the study.

Table 2 – Schedule of Assessments

Assessment	Baseline	Implant	Randomization	Discharge	Week 1 (\pm 3 days)	Month 1 ¹ (\pm 7 days)	Month 3 ¹ (\pm 30 days)	Month 6 ¹ (\pm 30 days)	Month 9 ¹ (\pm 30 Days)	Month 12 ¹ (\pm 30 days)	Every 6 months \pm 60 days thereafter	As Occurs/ Unscheduled
Inclusion/ Exclusion	X	X										
Informed Consent	X											
Demographics	X											

Clinical Investigation Plan

Assessment	Baseline	Implant	Randomization	Discharge	Week 1 (± 3 days)	Month 1 ¹ (± 7 days)	Month 3 ¹ (± 30 days)	Month 6 ¹ (± 30 days)	Month 9 ¹ (± 30 Days)	Month 12 ¹ (± 30 days)	Every 6 months ± 60 days thereafter	As Occurs/ Unscheduled
General and Cardiac Medical History	X											
Coagulation Assessment	X ⁴											
Right Heart Catheterization	X ²											X ⁴
Modified Rankin Score (MRS)	X											X
Incidental Use of Aspirin Containing Products	X			X	X	X	X	X	X	X	X	
Vital Signs	X			X	X	X	X	X	X	X	X	X
Laboratory Assessments	X ³				X	X	X	X	X	X	X	X ⁴
Anticoagulation/Antiplatelet Medications Log	X	X		X	X	X	X	X	X	X	X ⁹	X
Echocardiogram	X ²				X ⁴	X ⁴	X ⁴	X ⁴	X ⁴	X ⁴	X ⁴	X ⁵
Other Medications	X					X	X	X	X	X	X	X
Sample for Core Lab (ASA response, US only)	X						X	X		X		
QOL and Functional Capacity	X						X	X		X		
Implant Data		X										X ⁶
Enrollment	X ⁷											
Randomization			X									
Pump Parameters		X			X	X	X	X	X	X	X	X ⁵
Bottle Requisition via WebEZ			X				X	X	X	X	X	X ⁸
Bottle Dispensing/Return Log			X				X	X	X	X	X	X ⁸
Return Used Bottle to ALMAC for Accountability							X	X	X	X	X	X ⁸
Initial Discharge Data				X								
Cardiac Arrhythmias Assessment (e.g. EGM, EKG)	X				X	X	X	X	X	X	X	X
Subject Status					X	X	X	X	X	X	X	X ⁸
INR & LDH Log	X			X	X	X	X	X	X	X	X	X
Death												X
Withdrawal (early termination)												X
Transition to Open Label												X
Hospitalizations												X
Adverse Events												X
Device Deficiencies												X
Operative Procedures (excluding primary implant)												X

¹ For follow-up visit scheduling, one month = 30 days.

² Most recent results within 30 days prior to implant, if collected as SOC.

³ Most recent results obtained within 30 days prior to implant will be permitted as baseline data.

⁴ If performed as SOC.

⁵ At time of suspected thrombotic adverse event or pump exchange, if performed as SOC.

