Intervention	A radiopaque surgical marker (i.e., surgical clip) will be placed on the anterior surface of the aortic root midway between the sino-tubular ridge of the aorta and the ostia of the right coronary artery. The radiopaque marker will include placement of 2 standard surgical clips (manufacturer, size, picture; see Figures 1, 2A and B, 3 and 4) attached to the adventitia of the aorta and positioned as described above.
Assessments	Anteroposterior (AP) and lateral radiographs will be captured prior to discharge (but within 30 days of implant) and at the 3-month follow up visit. Radiographs will be obtained by a fixed radiography (fixed x-ray) and sent to the study sponsor in DICOM format. If standard of care (SOC), chest x-ray computed tomography (CT) scans will be obtained in addition to the radiographs.
References	

[figure not shown]
Clinical Investigation Plan

Figure 1: Acceptable Anteroposterior and Lateral Chest Radiograph Demonstrating Placement of a Radiopaque marker (two standard surgical clips). Clips are placed on the anterior surface of the aorta positioned halfway between the sino-tubular ridge of the aorta and the right coronary artery. Note: the full body of the HM3 is visible within the radiograph.

[figure not shown]
Clinical Investigation Plan

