Primary Endpoint Evaluation	The primary endpoint composite success rate will be calculated for each treatment arm based on the number of subjects who survive to 12 months with no primary endpoint events divided by the total number of subjects in the Modified Intention to Treat Population (mITT) population. The placebo arm will be considered non-inferior to the aspirin arm if the lower boundary of the one-sided 97.5% confidence limit of the risk difference in the composite success between treatment arms (Placebo-arm minus Aspirin-arm) is greater than the non-inferiority margin (10%).
Number of Subjects Required for Inclusion in Clinical Investigation	[REDACTED]
Secondary Endpoint	
• Non-surgical Major Hemorrhagic Events• Non-surgical Major Thrombotic Events• Survival• Stroke Rates,• Pump Thrombosis Rates• Bleeding Rates, including:
○ Non-surgical Bleeding○ Moderate Bleeding○ Severe Bleeding○ Fatal Bleeding○ GI Bleeding
Descriptive Endpoints	Hemocompatibility Score, Rehospitalizations, Economic Cost Implications

Clinical Investigation Plan

Subject Follow-up	
- Baseline- Implant- Randomization- Discharge- Week 1 ± 3 days- Month 1 ± 7 days- Month 3 ± 30 days- Month 6 ± 30 days- Month 9 ± 30 days- Month 12 ± 30 days- Every 6 month ± 60 days until last subject has completed the 12-month follow-up.
Inclusion Criteria	
• Subject will receive the HeartMate 3 per standard of care (SOC) in accordance with the approved indications for use in the country of implant.• Subject will receive the HeartMate 3 as their first durable VAD.• Subject must provide written informed consent prior to any clinical investigation related procedure.• In patients of child bearing capability, not currently pregnant and on appropriate contraception.

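### Device-position substudy: clusters defined by cannula change to month 3 are compared on outcomes that have no start time, so some outcomes precede the grouping

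*SAP*

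**What the plan says.** Protocol Appendix VI (Assessments) has the radiographs "captured prior to discharge (but within 30 days of implant) and at the 3-month follow up visit". SAP Appendix B, item 2 has an independent evaluator judge "potential significant change in position from pre-discharge to 3 months". Item 3 then adds: "Patients may also be grouped into clusters with each cluster representing different levels of change in cannula position".

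The outcomes to be compared between clusters include:
- "Adverse Events: Mortality, Stroke, Pump Thrombosis, Bleeding, Major HRAE, HRAE, Right Heart Failure, Cardiac Arrhythmia"
- "Index Hospitalization and ICU Length of Stay; All Cause readmission; Number of readmissions; Days out of the hospital vs in-hospital"
- major thrombotic and hemorrhagic events, right-heart-failure admissions, 6-minute walk, EQ-5D-5L and NYHA class.

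The month-3 window is "Month 3 ± 30 days" (Protocol Appendix VIII), and "For follow-up visit scheduling, one month = 30 days" (Protocol 6.3, Table 2, note 1).

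Appendix B states no date from which outcomes are counted, no landmark, no time-dependent exposure, and no rule for a subject without a second film. Protocol Appendix VI, primary objective 3, labels the link to outcomes exploratory. It names initial angulation as well as change, whereas SAP item 3 groups by change alone.

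**The concern.** Cluster membership is a fact about month 3, but the outcome list reaches back to the implant admission. Three problems follow.

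- **Index and ICU stay.** A stay that ends before the second film cannot result from a change measured at that film.
- **Non-fatal events before month 3.** A bleed or right heart failure in week 5 would be counted in a cluster assigned weeks later. If the event altered the position, the association would run from event to position.
- **Who can be classified.** A subject who dies, is transplanted or has the pump exchanged before the second film has no measurable change. Protocol 6.9.4 treats exchange as an explant outcome and collects nothing after the exchange procedure. The substudy rationale links malposition to pump thrombosis and stroke, so some early events of most interest drop out.

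At stake is whether a difference between clusters can be read as something that follows a change in position. Item 3 ends by inviting a reading of clinical significance and carries no caveat about timing.

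**Working it through.** The plan gives no figure for this comparison (no number of clusters, event rate or power), so there is nothing to reproduce. The check sets out the timing and then gives a size under stated assumptions.

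**1. When the cluster is known.** Month 3 = 3 × 30 = day 90. With ±30 days, the second film falls on day 60 to 120. As a share of 360 days, 60/360 = 17%, 90/360 = 25% and 120/360 = 33% precede it.

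**2. Share of first-year outcomes before the film.** Inputs are from Protocol 1.1.1 (MOMENTUM 3, HM3 arm): 79.0% two-year survival and 43.7% bleeding. Assumptions: constant hazards, and 43.7% read as a two-year cumulative proportion with a first bleed.
- Death hazard = −ln(0.79)/2 = 0.118 per year. One-year mortality = 1 − exp(−0.118) = 11.1%. By day 60, 90 and 120: 1.95%, 2.90% and 3.85%, or 17%, 26% and 35% of first-year deaths.
- Bleeding hazard = −ln(1 − 0.437)/2 = 0.287 per year. One-year first bleed = 25.0%. By day 60, 90 and 120: 4.67%, 6.93% and 9.13%, or 19%, 28% and 37% of first-year first bleeds.

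These count from implant. Protocol 5.5 withdraws subjects with an outcome up to day 14, so the relevant shares would be somewhat smaller.

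**3. Mortality, only subjects with both films clustered.** Film at day 90, and change has no effect on later death. Mortality from film to one year = 1 − exp(−0.118 × 0.75) = 8.5% in every cluster. The risk ratio between clusters is 8.5/8.5 = 1.00. The absolute figure is below the whole-cohort 11.1%, because it describes month-3 survivors.

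**4. Mortality, subjects without a second film placed in a no-change cluster.** Survival to day 90 is S = 0.971. Let p be the share of filmed subjects who show change (assumed).

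Mortality in no change = [S(1 − p) × 0.0846 + (1 − S)] / [S(1 − p) + (1 − S)]

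| p | Change | No change | Risk ratio |
|---|---|---|---|
| 20% | 8.46% | 11.76% | 0.72 |
| 30% | 8.46% | 12.21% | 0.69 |
| 50% | 8.46% | 13.63% | 0.62 |

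The true ratio is 1.00, so under this handling the departure is immortal-time bias.

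**5. Bleeds counted from implant, early bleed alters position.** Early bleed risk e = 6.93%. Later risk l = 1 − exp(−0.287 × 0.75) = 19.4%, the same in both clusters. The chance of change is 30% without an early bleed and q with one (both assumed). Example with q = 50%:
- P(change) = 0.0693 × 0.5 + 0.9307 × 0.3 = 0.314.
- Early bleed share: 0.0347/0.314 = 11.0% in change, 0.0347/0.686 = 5.1% in no change.
- One-year bleed: 0.110 + 0.890 × 0.194 = 28.3% against 0.051 + 0.949 × 0.194 = 23.5%. Risk ratio 1.21.

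With q = 40% the ratio is 1.10, and with q = 60% it is 1.32. If only bleeds after the film are counted, in subjects free of a bleed at the film, the risk is 19.4% in both clusters and the ratio is 1.00.

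**The case against.** The strongest reply has four parts.

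- **Standing of the analysis.** The SAP says only that clusters may be formed, the protocol calls the outcome comparison exploratory, and the substudy is observational, at up to 10 centers. Its main purpose is to validate a surgical clip as a landmark. No primary or secondary endpoint of the trial is touched. All of this stands and keeps the point minor.
- **Immortal time.** A reader might infer that the plan builds immortal-time bias into the mortality comparison. The documents do not support that. If only subjects with both films are clustered, every cluster shares the same survival period and the contrast is not distorted by it (step 3). The bias needs unfilmed subjects to be put in a cluster. Appendix B neither says this nor rules it out. Item 2 reports visual categories as a percentage of everyone in the substudy, which leaves the handling open. The SAP's missing-data section (2.7) is redacted and may address missing films, although a missing-data rule would not set when outcome counting begins.
- **Meaning of the shares.** The 17% to 35% of deaths in step 2 measures how many fall outside the comparison. It does not measure distortion between clusters.
- **Reverse causation.** No passage says that a bleed or right heart failure moves the cannula. The rationale argues only from position to outcome. The ratios in step 5 rest on assumed probabilities and show what could happen. What the text does establish is the ambiguous time order, and that holds however missing films are handled.

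**Conclusion.** The point holds as a minor, inexpensive improvement. As written, item 3 allows outcomes to precede the variable that defines the groups. This is clearest for "Index Hospitalization and ICU Length of Stay", which will usually be complete before the second film. That is an inference from film timing, since the documents give no length-of-stay distribution. It also applies to non-fatal events before month 3, which span 17% to 33% of a 360-day follow-up. Most of the follow-up comes after the film and is unaffected.

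The comparison is restricted to month-3 survivors with both films, so absolute mortality would be understated (8.5% against 11.1% under a constant hazard). Bias in the contrast between clusters is conditional: a risk ratio of 0.62 to 0.72 under no effect if unfilmed subjects were treated as unchanged, and 1.10 to 1.32 if early bleeds alter position to the degree assumed. The plan does not guard against either, but neither is built in.

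**What to change.** Amend SAP Appendix B, item 3:

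1. For change-based clusters, include only subjects with both films. Count mortality, adverse events and readmissions only after the date of the month-3 film (a landmark).
2. Keep functional measures from the month-3 visit but label them concurrent with the change. Protocol 6.8 lets one visit's assessments fall on different dates, so a strict cut at the film date would discard valid tests. Treat later measures as outcomes.
3. Drop index and ICU stay as outcomes of change, or relate them to initial position descriptively only. Part of the ICU stay may precede even the first film.
4. Add initial angulation, which the protocol objective names, as a separate grouping, with outcomes counted after the first film.
5. Report how many subjects lack a second film, with reasons (death, exchange, transplant, missed).
6. Describe results as exploratory association. A landmark restores time order but does not remove confounding, for example when an early bleed predicts a later one.

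The cost is appendix wording, with no new data collection. The downside is fewer events in the change-based comparison.

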Laboratory Assessments ¹	Hemoglobin (Hgb), Hematocrit (Hct), White Blood Cell Count (WBC), Platelets (PLT), Creatinine (Cr), Estimated Glomerular Filtration Rate (eGFR), LDH and INR, liver function tests (AST, ALT, total bilirubin, albumin, pre-albumin), blood urea nitrogen (BUN) Collected only if SOC: Activated Partial Thromboplastin Time (aPTT), Partial Thromboplastin Time (PTT), Plasma free Hgb (PHgb), D-Dimers, P Selectin, and fibrinogen. For diabetic patients: HbA1c, brain natriuretic peptide (BNP) or N-terminal pro-BNP (NT-pro-BNP) and fasting glucose
Coagulation Assessment ²	Collected only if prior testing performed or SOC: Tests may include but are not limited to HIT, protein C deficiency, protein S deficiency, antithrombin deficiency, plasminogen deficiency, lupus anticoagulant, factor V Leiden, prothrombin G20210A mutation, and primary antiphospholipid syndrome
Right Heart Catheterization ²	Central venous pressure (CVP) or right atrial pressure (RAP), systolic, diastolic and mean pulmonary artery pressure (PAS, PAD, PAM), pulmonary capillary wedge pressure (PCWP), cardiac output (CO), and cardiac index (CI)
Echocardiogram ²	Type of assessment, LVEF, LVEDD, LVESD, AI, MR, TR, PR, including severity and/or grade, and presence of LV or LA thrombus, and aortic valve opening ratio
QOL and Functional Capacity	EQ-5D-5L, 6-minute Walk Test (if subject is able, reason must be provided if not performed), NYHA Class, INTERMACS Profile

¹ Most recent results obtained within 30 days prior to implant will be permitted as baseline data.

² If collected per standard of care, most recent results within 30 days prior to implant.

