
Clinical Investigation Plan

[figure not shown]
	
The hypothesis of this sub-study is to develop and validate a surgical marker to serve as a consistent anatomical landmark to allow for accurate evaluation of the HeartMate 3 inflow canula position at the time of implant and subsequently, over time. We further hypothesize that differences in inflow canula positions and their changes over time may correlate with clinical outcomes.

Primary Objectives	
To develop and validate the use of a radiopaque surgical marker placed on the anterior surface of the aortic root below the sino-tubular ridge of the aorta just above the ostia of the right coronary artery to be used as a surrogate anatomical reference or landmark to more optimally assess HeartMate 3 inflow cannula position. Validation will be performed by assessing:
 
 1. The safety and feasibility of placing and visualizing the radiopaque marker; 2. The variation in cannula angulation relative to the radiopaque marker and cannula positional changes over time; 3. The relationship between the initial cannula angulation or its change over time with adverse clinical outcomes and functional capacity, as an exploratory analysis.
Study Populations	Subjects enrolled in the ARIES HM3 study who also meet eligibility requirements for this substudy at participating centers.
Study Design	Multi-center, prospective, non-controlled, non-randomized, observational sub-study within ARIES
Number of Subjects	Per ARIES HM3 study
Number of Centers	Up to 10 Centers
Duration of Subject Participation	Per ARIES HM3 study
Inclusion Criteria	
 1. Subjects enrolled within the ARIES HM3 study.
Exclusion Criteria	
 1. In the judgement of the implanting surgeon, that placement of the radiopaque surgical marker would have unacceptable risk based upon technical reasons or patient anatomy. 2. Subjects undergoing placement of the HeartMate 3 device through a minimally-invasive approach where sternotomy or upper sternotomy will not be performed and access to the anterior surface of the aorta below the sino-tubular ridge is not feasible.

Clinical Investigation Plan

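### SAP Appendix B compares outcomes between non-randomised clusters of cannula movement, plans no adjustment for baseline confounders or centre, and reads clinical significance from the result

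*SAP*

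**What the plan says.** Protocol Appendix VI describes the design as "Multi-center, prospective, non-controlled, non-randomized, observational sub-study within ARIES". Its third validation objective is "The relationship between the initial cannula angulation or its change over time with adverse clinical outcomes and functional capacity, as an exploratory analysis", and its hypothesis is that "differences in inflow canula positions and their changes over time may correlate with clinical outcomes".

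SAP Appendix B, item 3, puts this into practice: "Patients may also be grouped into clusters with each cluster representing different levels of change in cannula position". It continues: "Comparisons of adverse clinical outcomes and functional capacity including the following will be made between clusters". The outcomes listed include mortality, stroke, pump thrombosis, bleeding, right heart failure, index length of stay, readmission, six-minute walk, EQ-5D-5L and NYHA class. One further item reads "Effect of Treatment Arm designation on AEs as Sensitivity Analysis". The item closes: "Clinical significance can then be interpreted with the results of comparison".

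Appendix B names no test, regression model, baseline covariate, stratification or centre term for these comparisons. The appendix shows no redaction, so the silence appears to be the plan's own. The word exploratory, used in the protocol, does not appear in it.

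**The concern.** How far a cannula moves is not assigned at random. Illness severity, ventricular size and body size can plausibly influence both cannula position and outcomes such as death, right heart failure, readmission or walk distance, although the documents do not quantify this. Centre is a more direct route. Protocol Appendix VI itself gives surgical placement as one cause of malposition, the substudy runs at no more than 10 centres, and one or two of them could dominate a cluster.

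The only other factor the SAP considers is treatment arm. Arm is randomised, so it is the factor least likely to confound. If the comparison is made with nothing further, a difference between clusters cannot be separated from a difference in the patients or centres that make them up. The closing sentence nevertheless invites a clinical reading. At stake is whether the substudy reports cannula movement as a marker of poor outcome when it is not, or misses it when it is.

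**Working it through.** **No plan figure to reproduce.** The substudy states no sample size of its own, and no alpha, power, event rate or cluster size. The numbers in steps 1 and 2 are illustrations under assumed inputs. Step 3 applies document rates to an assumed sample size.

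**1. Crude risk ratio when movement has no effect.** Suppose a binary baseline factor multiplies event risk by R and is present in a proportion p_high of the high-movement cluster and p_low of the low-movement cluster. Then

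crude RR = [1 + p_high(R − 1)] / [1 + p_low(R − 1)]

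| p_high | p_low | R | Crude RR |
|---|---|---|---|
| 0.60 | 0.30 | 2 | 1.6/1.3 = 1.23 |
| 0.70 | 0.20 | 2 | 1.7/1.2 = 1.42 |
| 0.70 | 0.20 | 3 | 2.4/1.4 = 1.71 |

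**2. Milder confounding and false positives.** Take prevalence 30% in one cluster and 40%, 50% or 60% in the other. Take event risks without and with the factor of 20%/30%, 20%/40% or 30%/50%. Crude risk = r0 + (r1 − r0) × prevalence. The extremes are 24%/23% (RR 1.04, difference 1 point) and 32%/26% (RR 1.23, difference 6 points). Simulated two-sided 5% tests, 20,000 runs per scenario, with no true association:

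| Per cluster | Crude test | Stratified on the factor |
|---|---|---|
| 50 | 5.3% to 10.4% | 4.7% to 5.2% |
| 100 | 5.5% to 15.5% | 4.8% to 5.2% |
| 150 | 5.5% to 21.0% | 4.9% to 5.1% |

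The crude rate rises with sample size because the error is bias, not noise. Stratifying on the factor returns it to about 5%. Only one factor was modelled; several together could add up or offset each other.

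**3. How many subjects and events adjustment could use.** Spreading 628 subjects (Protocol 5.7) evenly over 50 centres and taking 10 gives 628/50 × 10 ≈ 126. This is an assumption: both centre counts are upper limits, and Protocol 5.7 lets one site randomise up to 15%, or 0.15 × 628 ≈ 94, without sponsor authorisation. As a rough guide, apply the 2-year rates for this pump in Protocol 1.1.1:

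- suspected pump thrombosis: 1.4% × 126 ≈ 2 subjects
- stroke: 9.9% × 126 ≈ 12 subjects

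A model with several covariates and up to 10 centres cannot be estimated reliably from such counts.

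**4. Which covariates exist.** Protocol Table 3 (section 6.4) collects age, height, INTERMACS profile and weight in all subjects. The echocardiogram row, "Type of assessment, LVEF, LVEDD, LVESD, AI, MR, TR, PR, including severity and/or grade", carries LVEDD, but its footnote limits it to results obtained as standard of care, so some values will be missing.

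**5. Timing.** Appendix B schedules radiographs before discharge (within 30 days of implant) and at 3 months, so change in position is known only at the second film. Index length of stay largely precedes that film. A patient who dies before it cannot be placed in a cluster. An early event may also affect position rather than follow from it. Covariate adjustment does not remove these problems.

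**The case against.** The best reply is that the protocol already gives this objective the right status. Appendix VI labels it exploratory, frames the hypothesis as correlation, and says the substudy does not affect the trial's main objectives. The clustering is optional, and the first two validation items are descriptive and untouched. All of that stands, and it keeps the point small. It does not remove the point, because the SAP appendix omits the label, gives the comparison no protection and ends on clinical significance.

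A reader might go further and infer that the SAP commits to an unadjusted analysis, or claims that cannula position causes outcomes. The documents do not support either. Appendix B is silent on method, includes a treatment-arm sensitivity item, and nowhere asserts a causal effect.

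A reader might also infer that confounding would be as large as most differences the substudy could report. That does not follow. With two assumed clusters of 63 and 30% risk in one, the other needs about 47% for two-sided 5% significance: pooled risk 0.385, standard error √(0.385 × 0.615 × 2/63) ≈ 0.087, and 0.17/0.087 ≈ 1.96. That is a risk ratio of about 0.47/0.30 = 1.57. Of the illustrative values, 1.23 and 1.42 fall below it and only 1.71 exceeds it.

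Finally, full adjustment for every outcome would be the wrong cure. Rare events cannot support it, LVEDD will be incomplete, and a centre term may remove some of the variation in position that surgical technique produces. These objections are sound and shape the fix.

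**Conclusion.** The concern holds in a limited form. Followed as written, item 3 gives a comparison of non-randomised clusters with no planned adjustment for baseline confounders or centre, and a closing sentence stronger than the protocol's exploratory, correlational framing. Severity, heart size or centre technique could therefore appear as an association with cannula movement.

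The size of that bias cannot be derived from the documents. The risk ratios and false-positive rates above show only how the bias would behave under assumed prevalences, risks and cluster sizes. The timing problem is separate and needs its own remedy. This is a worthwhile, low-cost improvement to a secondary part of the plan. It has no bearing on the trial's primary conclusion.

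**What to change.** In SAP Appendix B, item 3:

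- State that the comparisons are exploratory, as Protocol Appendix VI does.
- Where event counts allow (for example six-minute walk, EQ-5D-5L, readmission, bleeding), report beside the crude comparison an estimate adjusted for age, INTERMACS profile and body size, with centre as a random effect or stratum.
- Use baseline LVEDD as a sensitivity covariate, with a stated rule for missing values.
- Leave rare outcomes such as pump thrombosis and stroke descriptive.
- Where clusters are based on change to 3 months, count outcomes from the date of the 3-month radiograph. Describe index length of stay and earlier deaths separately.
- Replace the closing sentence with wording that the results are hypothesis-generating associations.

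The cost is SAP wording and a modest amount of extra analysis; no new data are needed. The downsides are some missing LVEDD, too few events for some outcomes, loss of events before the 3-month film, and possible removal of technique-related variation by the centre term. Showing crude and adjusted results together lets the reader judge that last effect.
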